 - v. Participant will stand with either their prosthetic foot or non-amputated foot on a rocker-board (as shown in Fig. 17) and the other foot on firm ground for 30-60 second.

Fig. 17: StrongTek Professional Wooden Balance Board used in the experimental procedure.

- vi. The participant will complete two trials of the task with each foot with a minimum of four repetitions per trial.
- vii. The number of repetitions may increase across days, as prescribed by the physical therapist, up to a maximum of 30 repetitions per day.
- viii. Between trials a stool will be provided to allow the participant to sit and rest until they are ready to resume.
- j. Stool stepping
 - i. Participant stands in front of a stool (seen in Fig. 18) of approximately 4-8in height with handrails to either side to offer support.

Fig. 18: KLB Sport 31" Adjustable Workout Aerobic Stepper used in the experimental procedure.

- ii. Participant is instructed to step their non-prosthetic limb onto the stool, hold it there for approximately 2-3 seconds, then step back down off of the stool.
- iii. Between trials a stool will be provided to allow the participant to sit and rest until they are ready to resume.

- k. Stop and go walking
 - i. While wearing safety harness, the participant will start by standing on the treadmill with feet shoulder width apart and with one foot on each belt of the treadmill.
 - ii. The participant will be given a 1 minute warmup trial of normal walking at their preferred walking speed.
 - iii. After the warmup the participant will be given a stool or chair to sit in and a rest period of at least 1 minute.
 - iv. After the rest period the stool/chair will be removed and the participant will again stand.
 - v. For each trial of the stop and go walking task:
 - 1. The participant will walk at their preferred walking speed
 - 2. After a predetermined amount of time between 20-40 seconds, a researcher will abruptly stop the treadmill.
 - 3. The treadmill will remain stopped for at least 20 seconds, or however long it takes for the participant to steady themselves and move into the standing position.
 - 4. The researcher will resume the treadmill at the preferred walking speed for 20-40 more seconds.
 - 5. The researcher will abruptly stop the treadmill again and allow at least 20 seconds for the participant to steady themselves again.
 - 6. The trial will end once the participant steadies themselves and is standing without assistance from handrails.
 - vi. There will be up to 10 trials over the course of the visit, with 2 minutes of rest between each trial.
- l. Arise from chair is part of the Amputee Mobility Predictor (AMP) Assessment and is used alongside a series of other mobility tasks to quantify the overall mobility of an amputee.
 - i. Participant is instructed to sit in a chair with the seat at a height between 40-50cm.
 - ii. Participant is instructed to cross arms over chest.
 - iii. Participant is instructed to stand up. Their performance is scored from 0-2 as follows:
 - 1. Unable to stand without assistance (score = 0)
 - 2. Able to stand but requiring multiple attempts (score = 1)
 - 3. Able to rise in a single attempt (score = 2)
- m. Standing Reach Task is part of the AMP Assessment and is a clinical evaluation for determining the range of a participant's dynamic balance.
 - i. Participant will stand on the treadmill while wearing the safety harness, keeping feet shoulder width apart and one foot on each belt of the treadmill.
 - ii. Participant will wear safety harness and have arm rails available for support.
 - iii. The participant will be instructed to raise their dominant arm 90 degrees in front of them while continuing to stand straight.

- iv. A researcher will stand off of the treadmill in front of the participant and hold a ruler 12 inches from the participant's extended hand. The ruler will be aligned midline to the sternum.
- v. The participant will be instructed to lean forward and grasp the ruler.
- vi. the participant's performance will be evaluated on a score of 0-2 as follows:
 - 1. Unable to grasp ruler (score = 0)
 - 2. Able, but requires use of arms for support (score = 1)
 - 3. Able without arm support (score = 2)
- n. EMG electrodes remove
 - i. This is done following the procedure mentioned in visit 2, step c.
- o. Protection harness remove
 - i. This is done following the procedure mentioned in visit 3-4, step o.
- p. Discuss the participants about their expectation of the next visit
 - i. A researcher will describe what will be done in the next visit and ask the participants to inform the research team if any issues are noticed.
- 6. Twelfth-thirteenth visit (duplicate of Third and fourth visit). These visits are used to evaluate the impact of the training program on the performance of the participants to conduct tasks which are not included in the training procedure. Each participant will conduct the task with both passive and powered prosthetic legs on different days.
- 7. Fourteenth-fifteenth visits (duplicate of Third and fourth visit). These visits are used to understand the long term effects of the training program on the participants. These visits will be conducted three months after the 13th visits.

Devices Used in the Research:

- Powered ankle prosthesis
 - This is a custom built minimal risk device shown in Fig. 1.
 - The device is designed so that no moving parts are directly attached to the user's prosthetic socket.
 - This minimizes risk of personal injury and damage to the socket
 - The procedure for putting on this device is described in the second visit, step a.
 - Safety precautions, such as the fall prevention suit and handrails used throughout the study, will ensure the risk of falls while using the device is minimal.
- Disturbance system
 - This is a custom built minimal risk device illustrated in Fig. 11.
 - The system is securely attached to the ceiling minimizing risk of it falling and causing damage
 - The weight used to generate the disturbance will never exceed 10% of the participant's body weight, minimizing risk that the disturbance will cause the participant to fall or stumble.
 - A light will flash before the disturbance occurs, ensuring the participant isn't caught off guard by the disturbance and can brace accordingly.
- Fall prevention suit
 - This device is off the shelf by not a medical device
 - This device is used on label and as approved

- This device is being used simply as a tool for fall prevention.
 - The procedure to put on this device is shown in Fig. 5.
- Instrumented treadmill (Registered Establishment Number: 1530895)
 - The device is off the shelf
 - The device is used on label and as approved
 - The device is being used simply as a tool for data collection in the research
 - The device is fixed on the ground and the participants will step on it after the treadmill is powered up. The participants will step off before the treadmill is powered off.
- VICON motion capture system (Registered Establishment Number: [1000377231](#))
 - The device is off the shelf
 - The device is used on label and as approved
 - The device is being used as a tool to collect data about body movement based on reflected markers which are attached to body segment
 - The device includes a series of cameras and does not contact with the participants
- AMBU Neuraline 715 (Registered Establishment Number: 3004040397)
 - The device is off the shelf
 - The device is used on label and as approved
 - The device is used to collect EMG signals from muscles on human body
 - The device has a self-adhesive cover and can be mounted on the skin of body segment directly. Cleaning of the skin surface using alcohol pads are needed.
- M400 diagnostic EMG system from Motion lab system
 - The device is off the shelf
 - The device is used on label and as approved
 - The device is being used as a tool to collect EMG data from muscles on the body segment
 - The device is attached with the EMG electrodes and does not contact with the human body directly.
- Aeromats
 - This device is off the shelf by not a medical device
 - This device is used on label and as approved
 - This device is being used simply as a platform for participants to stand on it.
 - This device can be put on the floor directly.
- The Step Adjustable High Step Aerobic Platform
 - This device is off the shelf by not a medical device
 - This device is used on label and as approved
 - This device is being used simply as a platform for participants to stand on.
 - This device can be put on the floor directly.
- Element Fitness Slanted Step Risers
 - This device is off the shelf by not a medical device
 - This device is used on label and as approved
 - This device is being used to place the previously mentioned “The Step Adjustable High Step Aerobic Platform” at an inclined angle.

- This device can be put on the floor directly.
- KLB Sport 31" Adjustable Workout Aerobic Stepper
 - This device is off the shelf by not a medical device
 - This device is used on label and as approved
 - This device is being used simply as a platform for participants to step on it.
 - This device can be put on the floor directly.
- StrongTek Professional Wooden Balance Board
 - This device is off the shelf by not a medical device
 - This device is used on label and as approved
 - This device is being used simply as a platform for participants to step on it.
 - This device can be put on the floor directly.

Risks Associated with each lab activity:

- Participants are exposed to the risk of pressure ulcers. This risk is unlikely. This risk comes from activities during visits 2-15 when EMG electrodes are used inside the socket.
 - The risks from these activities are mitigated by
 - Recruitment of participants who are used a socket with good fit;
 - Using EMG electrodes with very low profiles, less than 1mm thickness and soft
 - inspecting any potential skin damage before and after if the EMG electrodes are used..
- Participants are exposed to low risk of fatigue and/or muscle soreness. This risk comes from activities during visits 2-15.
 - The risk from these activities are mitigated by
 - control the efforts of the participants by limiting length of each task
 - provide rests between tasks
 - permit the participants to end the experiments whenever they feel the fatigue or the sore muscle.
 - the clinicians will recommend skipping or combining tasks and visits based on the participants' situation to prevent fatigue and unnecessary training repeat (some participants may quickly reach their maximum capability, then additional training becomes unnecessary).
- Participants are exposed to the risk of fall. This risk is unlikely. This risk comes from activities during visits 2-15 when the activities are not conducted in a sitting position, or during the movement from one activity to another one.
 - The risks from these activities are mitigated by
 - provide fall protection harness during the experimental procedure
 - provide handrail or walker when the harness is not practical
- Participants are exposed to low risk of identity leak. This risk comes from these activities: screening, scheduling, and payment procedure. The risks from these activities are mitigated by
 - all the participants will be given a code name, so their name is not linked with any saved data;

- the name and contact information will be written down in a master list, which is locked in the PI's office and are accessible to PI only;
- the W9 form and direct deposit setup is done through the standard procedure defined by NCSU, the research team does not collect sensitive information, such as SSN;
- the payment form will be transferred to the department immediately after the experimental procedure; and
- destroying all the contact information, which are recorded on the master list, at the end of the project, by shredding.

Compensation:

- Each participant will be paid \$25/hour with a minimum 2 hour for a visit. If the participant decides to quit the experimental procedure, they will be paid based on the \$25 per hour that they spent with the research team or \$50. The one with the higher number will be used.
- Travel cost of the participant will also be reimbursed. If the round trip from the participants' home to our testing site is longer than 30 minutes, the study subjects will be paid for their travel time. The travel time will be rounded to the nearest 15 mins. One hour travel time will be counted as 1.6 hour experimental time if participants' vehicles are used for commuting. The round trip time will be calculated using Google Map from the home address of the participant to [name]. If the paid travel time leads to a lower payment compared with what is calculated based on the University approved standard mileage rate, the later one will be used.

Data Access and Security Plan Needed: No, Data are yellow. Sensitive data is not handled by the research team and is instead given right to the accounting office by the participant.

Is this a Clinical Trial: Yes, this is studying a health related outcome with an intervention.

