Project Title:

Toward Restoration of Normative Postural Control and
Stability using Neural Control of Powered Prosthetic
Ankles

Protocol Number: 26076

Protocol is approved by NC State University IRB

Approval Period:

07/14/23 – 07/13/24

Updated on: 03/18/2024

Number of Participants:

- 50 unilateral transtibial amputees (below the knee amputation)

Inclusion/Exclusion:

- AMPUTEE ELIGIBILITY
 - 18 years or older
 - unilateral bower limb amputee
 - K-level 2 or higher (who are frequent prosthesis users and may benefit from the proposed prosthesis training and use of dEMG controlled powered prosthesis)
 - Amputation occurred over 2 years ago
 - At least 1 year of experience using their prosthetic leg
 - Has used the current socket for at least 6 months without a significant skin issue or major modification.
 - Are willing to come to NC State University's Centennial Campus to participate in research and be photographed while doing research activities
- AMPUTEE INELIGIBILITY
 - have a very short residual shank (the length of the residual limb is $\leq 15\%$ of the length of intact limb)
 - cannot perform functional ambulation in the community on a daily basis without assistive devices
 - Cognitive or visual impairment that affects the participant's ability to provide informed consent or to follow simple instructions during the experiments
 - Congenital amputees
 - Amputees who use powered prosthetic ankles
 - Weight more than 300lbs
 - Pregnant Person
 - Allergic to latex, which is often contained in medical tapes.
- Reasons for the inclusion and exclusion criteria:
 - We would like to involve participants, who are capable to walk in the community without additional assistive devices.
 - To ensure that there is enough muscles on their residual limb for EMG data collection, we would like to exclude those who have very short residual limbs. Congenital amputees are also excluded due to the fact that they may never develop the needed muscle patterns on their residual limb.
 - To ensure their safety, we need them to have a healthy residual limb with low risk of pressure ulcer (young amputees, pregnant people, and recent amputees usually have high risk of pressure ulcers).
 - Users of powered prosthetic ankle is excluded due to the fact that they could not be used for the comparison group and may cause bias in the randomization.
 - The safety harness has a limit of 300lbs, which is used to limit the maximum weight of the participants.

Recruitment:

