- 3. Third and fourth visits: baseline evaluation with powered prosthesis and passive prosthesis. Each participant will finish the two visits. One of the visits is dedicated to their own passive prosthesis and the other visit is for the powered prosthesis. The sequence of the evaluation is randomized. The tasks conducted in the two visits are generally identical. The only difference is that one of the visits uses the participants' everyday prosthetic foot and the other uses the powered prosthetic ankle (shown in Fig. 1)
 - a. Checking EMG site
 - i. One experimenter visually inspects the locations, where the EMG electrodes are placed to identify any bruise
 - ii. Ask the participants whether they feel anything abnormal on their residual limb since the start of the experimental procedure.
 - iii. The visit is canceled if a bruise is noticed.
 - b. Verbal survey the participants about their comfort
 - i. The experimenter will ask the participants whether they felt unusual exhausting from the last training or evaluation session.
 - ii. The visit is canceled if the participant felt that it is to hard to finish the current test.
 - c. EMG mounting (only in powered prosthesis visit)
 - i. This is done following the procedure mentioned in visit 2, steps b.ii - b.vii.
 - d. Mount the powered prosthetic ankle (only in powered prosthesis visit)
 - i. A researcher will disconnect the prosthetic leg of the participants and mount the sockets with the powered prosthetic ankle, as shown in Fig. 1. The prosthetic ankle is designed with a bottom mounting point. By tightening the screws, shown in Fig. 2, a prosthetic socket can be fixed into the powered prosthetic ankle as shown in Fig. 1.

e. Protection harness mounting

- i. The participant will wear a fall prevention suit (Marine Anti-gravity System) in a standing position with help from the experimenters as shown in Fig. 5.
- ii. The research team has three systems with size (M, L, XL) for participants to choose from.
- iii. The railing used to connect the fall protection gear is designed to support a weight carry robot for rehabilitation training. Our participants are usually much lower weight compared with the limit of the robot system (250lbs), which makes it very safe for our purpose.

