- iv. Before the testing, the researcher will wear the protection gear and rely on the railing for body weight support at least for 3 seconds by using a shorter connection cable. It is a quick test of the reliability of the protection system. The harness will be cleaned using alcohol wipe and spray every time after usage.

f. Marker mounting

- i. identify the locations of markers on human body. Because the study will focus on the posture control, we will cover the motion of feet, shanks, thighs, torso, and head as seen in Fig. 6. For each body segments, we will mount no more than 5 markers with additional markers at hips, knees, ankles, and neck (two at each joint). So total less than 58 markers are adopted.

[figure not shown]

Fig.6: marker locations for the motion capture (dots shows the approximately marker locations).

- ii. reflective markers (no energy stored) from VICON (as shown in Fig. 7) will be used in the study. Before mounting, the participants are instructed to clean the mounting area by the research team using alcohol pads as shown in Fig. 4. Two types of mounting will be conducted based on the location of markers.
 1. Condition one: base plate mounting. The markers will be stucked on small plastic plates using double side tapes (as shown in Fig. 7a) by the research team in advance. Then a researcher will attach the plastic plate to the human body using a soft velcro strap.
 2. Condition two: direct mounting. The research team will put double side tapes (as shown in Fig. 7b) under the bases of the markers. Under the direction of the research team, the participant will push the marker toward their own body gently. Then a research team member will enhance the mounting with a medical tape shown in Fig. 8.

Fig. 7: a) the plastic plates used to host the markers and b) the marker is mounted on body skin directly.

Fig. 8: Medical tape used to stabilize the markers (0.5 inch width and 2.7 mil thickness)

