- ii. The researcher will mark off a space 3 meters in front of the chair.
- iii. The participant will start seated in the chair provided by the researcher.
- iv. At the researcher's instruction, the participant will stand up from the chair, walk to the marked spot 3 meters in front of them, turn around, walk back to the chair, and sit down.
- v. The researcher will start a time when they instruct the participant to stand, and end the timer when they sit back down.
- vi. (optional) Secondary tasks are often incorporated into TUG tests to increase utility of the test in identifying fall risks. We will be using an auditory stroop task to evaluate the cognitive load of the participant.
 1. While performing the TUG task, a speaker will sound a 500ms sound clip of the word "High" or "Low" in either a high pitch (360Hz) or a low pitch (180Hz), although these frequencies may be adjusted based on individual needs to ensure there is a clear distinction.

2. After each word is played, the participant will be asked to verbally respond with "High" or "Low" based on the pitch of the sound, but not the word spoken.
3. The speaker will produce new sound clips in random intervals of 2-3 seconds, the participant will respond after each sound clip. The number of sound clips and the number of correct responses are recorded for later analysis.

- i. Anticipated disturbance
 - i. The participant will stand on the treadmill with feet shoulder width apart, one foot on each belt, facing the perturbation platform as illustrated in Fig. 11.
 1. The platform delivers perturbations through a hanging weight which is a soft weight ball selected to be approximately 10% of the participant's body weight (BW) (± 5 lbs).
 2. The platform will be bolted to a rail, which is used for the patent protection, on the top of the treadmill.
 3. The weight is connected to a set of handlebars by 2 cords via a series of pulleys. An electromagnet is used in series with one of the cords to control the connection of the handlebars to the weight.
 4. When the electromagnet releases, the weight drops and causes the handlebars to either be pulled away from the participant or pushed towards them.
 5. An LED light at eye level with the participant will turn on exactly 1 second before the weight drops.
 6. The LED light will turn off exactly before the weight drops.
 7. Two different conditions will be tested:
 - a. Condition 1: 10% BW Push, the handlebars will be pushed towards the participant.

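### People weighing up to 300 lb are eligible on the strength of the harness limit, but the only figure given for the rail that holds the harness is a robot system's 250 lb limit

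*Protocol*

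**What the plan says.** Under Inclusion/Exclusion, the list of reasons for ineligibility contains "Weight more than 300lbs". The reasons given beneath it tie this cap to equipment: "The safety harness has a limit of 300lbs, which is used to limit the maximum weight of the participants".

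The rail is described in the third and fourth visits, step e (Protection harness mounting), item iii. Its origin is given as "The railing used to connect the fall protection gear is designed to support a weight carry robot for rehabilitation training", and the case for its safety follows: "Our participants are usually much lower weight compared with the limit of the robot system (250lbs), which makes it very safe for our purpose".

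Item iv of the same step adds a check before testing, in which "the researcher will wear the protection gear and rely on the railing for body weight support at least for 3 seconds", on a shortened connection cable. The researcher's weight is not given.

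Two other places bear on the point. The anticipated-disturbance task (step i, item i.2) says of the perturbation device: "The platform will be bolted to a rail, which is used for the patent protection, on the top of the treadmill". Under Risks Associated with each lab activity, the first mitigation for falls is to "provide fall protection harness during the experimental procedure".

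**The concern.** The protocol's own principle is that equipment capacity sets the weight ceiling. It applies that principle to the harness and stops there. A harness protects only as well as the cable and rail that hold it, so the ceiling should come from the weakest part of that chain. For the rail, the one number offered is lower than the ceiling.

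The safety sentence also describes the typical participant. An eligibility limit has to protect the heaviest person it admits, and for someone between 250 and 300 lb the sentence is untrue.

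What is at stake is fall arrest in people with a lower-limb amputation, some of them on a custom-built powered ankle, during tasks that deliberately challenge balance: maximal sway, weight-drop pushes and pulls, eyes-closed stance on foam and on an incline, single-limb balance on the prosthetic side, and abrupt treadmill stops. The point concerns eligibility and safety; no endpoint or analysis depends on it.

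**Working it through.** There is no calculated figure in the protocol to reproduce. The check compares the stated limits and then asks how often the gap could matter.

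**Inputs**

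| Item | Value | Where |
|---|---|---|
| Heaviest eligible participant | 300 lb | Inclusion/Exclusion, ineligibility list |
| Harness limit | 300 lb | Reasons for the criteria |
| Robot system limit, cited in support of the rail | 250 lb | Visits 3 and 4, step e.iii |
| Load rating of the rail | not stated | – |
| Load rating of the connection cable | not stated | – |
| Load in the pre-use check | one researcher's body weight, not stated, for at least 3 seconds | Visits 3 and 4, step e.iv |
| Planned participants | 50 | Number of Participants |

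**Gap between the limits**

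- Difference: 300 − 250 = 50 lb.
- Relative to the cited figure: 50 / 250 = 20%.
- This uses static body weight only. Arresting a fall adds dynamic load, for which the protocol gives no figure.

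**Does the pre-use check close the gap?** It shows that the rail held one researcher's weight for a few seconds. It would speak to 300 lb only if the researcher weighed that much, and the protocol does not require this.

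**Possible extra load.** If the perturbation platform is bolted to the same rail, its hanging weight for a 300 lb participant is about 0.10 × 300 = 30 lb, before the platform's own weight. The text does not settle whether it is the same rail: the disturbance task mentions a rail used for protection, while Devices Used in the Research says the system is attached to the ceiling.

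**How many people could be affected?** This needs the share *p* of eligible candidates weighing more than 250 and up to 300 lb, which the protocol does not give. Taking *p* from 1% to 10% as an assumption, with n = 50:

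- expected number = n × p
- chance of at least one = 1 − (1 − p)^50

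| Assumed p | Expected number | Chance of at least one |
|---|---|---|
| 1% | 0.5 | 1 − 0.99^50 = 0.395 |
| 2% | 1.0 | 1 − 0.98^50 = 0.636 |
| 5% | 2.5 | 1 − 0.95^50 = 0.923 |
| 10% | 5.0 | 1 − 0.90^50 = 0.995 |

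**The case against.** The strongest reply is that the two numbers belong to different things. The 250 lb is the limit of the robot system. The rail was built to carry that robot, and so presumably has to hold the robot's own weight as well as its load. On that reading the rail could well be good for 300 lb, and the fault is an undocumented rating, not two conflicting limits on one component. This stands as far as it goes: the protocol does not show that the rail is inadequate. But it does not make this argument either. It offers 250 lb as the reason the rail is safe and then admits people above it.

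A second reply is that making 250 lb the default cap turns the robot's limit into an eligibility rule and could exclude people needlessly. The cost is real. It lasts only until a rating is confirmed, and until then 250 lb is the only limit the protocol itself relies on.

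Third, the harness is not the only protection. Handrails or a walker are provided, a light warns of each perturbation, and participants may step to recover. These reduce reliance on the harness in some tasks but do not replace it.

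Fourth, the assumed 1% to 10% share has no support in the protocol and gives a range too wide to decide anything. That is fair; the 50 lb gap does not depend on it. It is also true that ratings may sit in equipment documents not shown, but the protocol's stated justification would still need correcting.

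**Conclusion.** The concern holds. The protocol admits people up to 50 lb (20%) above the only figure it uses to call the harness rail safe, and nothing else in it covers the range from 250 to 300 lb. The comparison rests on stated figures alone.

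Two things remain unknown. One is the rail's actual rating: if it covers 300 lb with allowance for fall loading, the defect is confined to the written justification; if it does not, the exclusion criterion is unsafe. The other is the number of people affected, which on the assumed shares ranges from 0.5 to 5 expected among 50.

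The point should be resolved before anyone above 250 lb is tested in the harness. Confidence is medium, because the hazard itself is not established.

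**What to change.** Set the weight exclusion at the lowest verified rated limit in the whole fall-arrest chain: harness, connection cable and rail. Confirm that the rating applies to arresting a fall and not only to a static load, and count the perturbation platform if it shares the rail. Until a rail rating covering 300 lb is confirmed, use 250 lb.

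State the resulting figure in three places: the exclusion criterion, its rationale, and step e.iii of the third and fourth visits. In step e.iii, replace the argument from typical participant weight with the rating itself. The researcher's hang test can stay as a functional check, but it should not be presented as evidence of capacity.

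The cost is a look-up of the rail and cable ratings and three edited lines. If the verified limit is below 300 lb, a few heavier candidates become ineligible. If it is 300 lb or more, nobody is lost.
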